## 1.0 Study Summary

**Setting:** This study will be conducted within and supported by the strong research infrastructure at Dartmouth-Hitchcock Medical Center and the Dartmouth Cancer Center, an NCI- designated Comprehensive Cancer.

**Purpose:** Supportive care, behavioral intervention development. This research proposes to evaluate a novel intervention approach to prescribing exercise to stage 0-III breast cancer survivors based on affect regulation. The novel intervention is called “Affect-Rx.”

**Primary Objective:** To modify and refine the Affect-Rx exercise prescription and study protocol to be acceptable for use with breast cancer survivors.

**Study Specific Aim (i.e., Aim 1):** To modify and refine the Affect-Rx exercise prescription and study protocol to be acceptable for use with breast cancer survivors. Modifications and refinements will be informed by semi-structured participant interviews and objective indicators of acceptability assessed using the Treatment Acceptability and Preferences (TAP) Measure, accelerometer wear-time, and daily EMA survey completion.

## 2.0 Background

**Exercise is medicine in cancer care, but participation is lacking.** The strategic plan set by the Health Behaviors Research Branch of the National Cancer Institute (NCI) identifies physical inactivity as a key cancer-related behavioral risk factor of interest. There is strong epidemiological evidence of a dose-response relationship between exercise post-cancer diagnosis and cancer-related mortality risk. While more exercise is better, even a modest amount of exercise produces a clinically meaningful reduction in cancer-related mortality. For breast cancer survivors, cancer-related mortality risk has been shown to decrease by 2.5% for every additional ~15 mins/week of at least moderate-intensity physical activity completed under a threshold of ~150 mins/week. The American College of Sports Medicine (ACSM) Exercise Guidelines for Cancer Survivors recommend all survivors avoid inactivity; the guidelines also state exercise is safe for most cancer survivors, and ≥ 90 mins/week of at least moderate-intensity physical activity is associated with strong reductions in cancer treatment- related adverse effects (e.g., fatigue) and improvements in physical functioning and health- related quality of life. However, few breast cancer survivors achieve these recommended guidelines, and rates of exercise engagement decline significantly starting from time of diagnosis, with most breast cancer survivors never fully returning to pre-diagnosis activity levels. Further, in rural areas, 50% of survivors engage in no leisure time physical activity.

**Among the general population, efforts to identify underlying determinants of physical activity have increasingly emphasized the contribution of affective (i.e., feeling- based) factors.** For example, the “affective response to exercise” (i.e., feelings of pleasure and arousal directly resulting from exercise) has been shown to predict adherence to exercise regimens over time. A 2015 systematic review found effect sizes ranging from  $r = .18$  to  $r = .51$  for the relationship between affective responses *during* exercise and future exercise. Also, “incidental affect” (i.e., feelings of pleasure and arousal, *not* directly resulting from any specific behavior), has been shown to predict daily variation in physical activity levels. The relationship between incidental affect and exercise is consistent with the “broaden-and-build theory of positive emotions,” which postulates more positive feelings experienced throughout the day enable individuals to expand their bio-psycho-social resources and increase approach motivation for effortful tasks (e.g., exercise). There is evidence that affective factors are amenable to influence by certain intervention strategies, however, the data pertaining to affective determinants of physical

activity among cancer survivors are currently limited to only a few investigations.

**The ACSM Guidance for Prescribing Exercise Position Stand calls for additional research on the use of “affect-regulated” exercise prescriptions for physically inactive samples.** Prescribing affect-regulated exercise involves instructing individuals to *exercise at the highest pace that still feels good.* The hedonic principle is the theoretical basis for this strategy: i.e., behavior that feels good is likely to be repeated. This approach is in contrast to standard-of-care intensity-regulated exercise prescriptions that instructs individuals to regulate pace during exercise based on heart rate to achieve a relative exercise intensity (e.g., 64-76% of max heart rate). Importantly, the affect-regulated prescription strategy is not simply a “hands-off” approach because studies have found that when physically inactive individuals are instructed to self-select their own pace of exercise, they do not prioritize feeling good by default.

**Why an affect-regulated exercise prescription?** While some individuals experience positive shifts in affective response during moderate-vigorous physical activity, it is well documented that many people – especially those who tend to be the targets of exercise intervention programming (i.e., individuals who are more aerobically deconditioned, inactive, or overweight) – experience intensity-prescribed exercise as highly unpleasant. Randomized studies have shown that compared to standard-of-care intensity-regulated prescriptions, affect-regulated prescriptions result in more pleasure during exercise (even when there is no statistically significant difference in actual intensity). Furthermore, several independent research groups have shown that affect-regulated exercise prescriptions can produce health benefits equivalent to those achieved from intensity-regulated exercise prescriptions, but with superior adherence rates over time (thus increasing potential for long-term health benefits) especially among those who are older and the most aerobically deconditioned.

**An affect-regulated exercise prescription may be useful for promoting exercise to physically inactive breast cancer survivors for several reasons:** Many breast cancer survivors are overweight or obese, which increases the likelihood that exercise is experienced as unpleasant. Further, peripheral neuropathy, a common chemotherapy-related adverse effect that can persist long after the conclusion of treatment, is another factor that may contribute to worse affective experiences during exercise. Beyond these patient-level characteristics, research has shown that even small improvements in affective response during exercise can yield changes in exercise behavior that would be clinically meaningful for cancer survivors. Specifically, one recent study used ecological momentary assessment (EMA) methods to measure affective responses to exercise in-real-time as participants completed structured exercise over 6-months. Results showed that a 1-unit increase on the Feeling Scale (e.g., moving from 0 = “neutral” to 1 = “fairly good”), resulted in approximately 90 extra minutes of moderate-vigorous physical activity one week later. Notably, a change of 90 extra exercise minutes per week would move a breast cancer survivor from ‘completely sedentary’ to ‘meeting ACSM recommended guidelines for weekly exercise’.

## 3.0 Study Endpoints

### Primary Outcomes:

1. Acceptability of the affect-regulated exercise prescription measured using the Treatment Acceptability and Preferences (TAP) Measure.

**Description:** A 4-item self-report questionnaire used to measure acceptability of the affect-regulated exercise prescription using a Likert scale ranging from 0 (not at all) to 4 (very much). Total scores range from 0 - 16. Higher scores indicate greater acceptability. **Time Frame:** 12-weeks follow-up assessment.

2. Proportion of sample with valid accelerometer data at baseline.

Description: The number of participants with valid accelerometer data out of the total number of participants in the sample at baseline. Time Frame: Baseline assessment

**3. Proportion of sample with valid accelerometer data at 2-weeks follow-up.**

Description: The number of participants with valid accelerometer data out of the total number of participants in the sample during the 2-week follow-up assessment. Time Frame: 2-weeks follow-up assessment

**4. Proportion of sample with valid accelerometer data at 6-weeks follow-up.**

Description: The number of participants with valid accelerometer data out of the total number of participants in the sample during the 6-week follow-up assessment. Time Frame: 6-weeks follow-up assessment

**5. Proportion of sample with valid accelerometer data at 12-weeks follow-up.**

Description: The number of participants with valid accelerometer data out of the total number of participants in the sample during the 12-week follow-up assessment. Time Frame: 12-weeks follow-up assessment

**6. Rate of ecological momentary assessment (EMA) survey prompt completion.**

Description: The number of Ecological momentary assessment (EMA) survey prompts completed by participants during the study out of the total number of EMA survey prompts delivered to participants. Time Frame: Baseline through 12-weeks follow-up assessments

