**How research material will be obtained and source materials:** The information collected for this study will only be used for the study as described. This will be made clear during the consent process and included in all written consent forms. Information about study participants will be kept confidential and managed according to the requirements of the Health Insurance Portability and Accountability Act of 1996 (HIPAA). Any identifiable participant information will be secured behind the D-H firewall on password-protected computers and servers. All participants enrolling will be entered into the OnCore software system for Clinical Trials, which is Dartmouth-Hitchcock's clinical trial monitoring software in real-time (i.e., once the participant is consented, they will subsequently be entered).

Clinical characteristics and variables will be collected by medical record extraction (breast cancer stage, prior treatment, and other co-morbidities). Questionnaire and demographic data will be collected using REDCap, a research data collection platform. REDCap (Research Electronic Data Capture) is a secure, web-based application designed to support data capture for research studies, providing: a) an intuitive interface for validated data entry; b) audit trails for tracking data manipulation and export procedures; c) automated export procedures for seamless data downloads to common statistical packages; and d) procedures for importing data from external sources.

Ecological momentary assessment (EMA) data will be collected using LifeData software via the RealLife Exp mobile app (Android and iOS compatible). This app will be installed on participants personal cell phones at the time of study enrollment. Once installed, the RealLife app will deliver daily EMAs over 10-day periods during the baseline, 2-, 6-, and 12-week follow-up assessments, concurrent with accelerometry data collection procedures. This EMA collection schedule was found to be acceptable to a sample of breast cancer survivors in a recent study. Daily EMAs will include: a morning report, within 2 hours of a participant's stated wake time, and 2 additional prompts during the afternoon and evening.

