Consistent with procedures established in the research team's prior work, participants will be expressly instructed to use the RealLife mobile app to indicate when they start an exercise session. The RealLife mobile app will prompt participants to complete ratings of affective response to exercise at the start, during, and end of exercise. Specifically, once participants indicate that they have started their exercise session, the app will send alerts to report on three variables [affective valence, measured via the Feeling Scale (FS), affective arousal, measured via the Felt Arousal Scale (FAS), and perceived exertion, measured via the Ratings of Perceived Exertion scale (RPE), every 5-minutes up until 30 minutes]. After 30 minutes, the app will send alerts to report on these three measures every 10 minutes. Participants will indicate when they have ended their exercise session and the app will send an alert to report on FS/FAS/RPE 10 minutes after the end of exercise is reported.

Exercise behavior will be measured in terms of minutes of moderate-vigorous physical activity measured by the ActiGraph wGT3X-BT accelerometer. Participants will be instructed to wear the research-grade ActiGraph accelerometer wGT3X-BT (ActiGraph, LLC) on their non-dominant hip during all waking hours, except when bathing or swimming, for 10 consecutive days during data collection periods at baseline and 2-, 6-, and 12-weeks follow-up. The research grade ActiGraph wGT3X-BT model is a valid measure of physical activity intensity and duration among multiple populations, including breast cancer survivors.

Participants will further be asked to record all periods of accelerometer non-wear time in a paper log and to describe reasons for non-wear (e.g., swimming, illness, etc.). If the accelerometer was not worn during times when they performed physical activity, participants will be asked to specify (in both the paper log and on the daily EMA assessments) what the activity was (e.g., swimming laps), the level of

effort (e.g., light, moderate, vigorous), and how long the activity was performed in minutes.

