**Participant Incentives:** Participant payments will be provided at a rate of \$20 for completing each of the REDCap surveys (i.e., T1 REDCap survey and T2 REDCap survey). Additionally, participants will be compensated \$1 for each of the morning report and random EMA prompts completed during the 10-day assessment periods at baseline, 2-, 6-, and 12-weeks follow-up; thus, a total of \$120 can be earned for completing EMA assessments (\$1 X 3 EMA prompts/day X 10 days X 4 data collection periods). (Note, participants will not be paid for completing the during exercise EMAs reports to avoid encouraging over-reporting of exercise). Each participant, can earn a total of \$160\* for completing all study assessments.

At the Tele- Visit 1 appointment, participants will also be given a Fitbit activity tracker (to keep) as compensation for their participation and to encourage behavioral self-monitoring as part of the core exercise intervention. If participants decide to terminate their participation in the study early (before the week 12 follow-up assessment), we will ask that they return the Fitbit monitor given to them at the Tele- Visit 1 appointment. In this case, we would provide them a pre-paid envelope and ask they follow instructions to mail the Fitbit back at their earliest convenience. This will be explained to participants during the consent process.

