## 13.0 Withdrawal of Subjects

Participants will be withdrawn from the study at their request. The research team will continue attempts to contact participants for each session and study assessment unless and until they ask us to stop/express the desire to withdraw. Each study contact is an extension of informed consent where participants are told what is occurring, what happens next, and that their participation is voluntary. When we are unable to reach participants by telephone for at least 14 days we send a letter conveying our attempts to reach them and ask them to contact us to continue with study activities or withdraw, as they prefer. Participants may be withdrawn from the research without their consent if they experience any medical events (after enrollment) that would make it unsafe for them to continue participation in an unsupervised exercise intervention (e.g., myocardial infarction).

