## 16.0 Statistical Analysis Plan

**Analysis Plan & Power Analysis:** There are no definitive guidelines for determining the size of a pilot study in healthcare research, and, according to guidelines provided by ORBIT, for this early phase of intervention development, "*The sample size can be small because clinical, not statistical, benefit is sought and sample size calculations are unnecessary*" (pg. 977). Nevertheless, our target sample size of

*N* = 20 intervention completers is consistent with typical sample size targets used in similar early-phase open pilot studies.

**Aim 1 (ORBIT Phase Ib).** To modify and refine the Affect-Rx exercise prescription and study protocol to be acceptable for use with breast cancer survivors. Modifications and refinements will be informed by semi-structured participant interviews and objective indicators of acceptability assessed using the Treatment Acceptability and Preferences (TAP) Measure, accelerometer wear-time, and daily EMA survey completion.

**Analysis of Aim 1 Quantitative Data:** Responses to the Treatment Acceptability and Preferences TAP Measure will be scored, distributions will be examined, and data will be assessed for completeness. Rates of accelerometer wear-time compliance and daily ecological momentary assessment (EMA) completion will similarly be examined for completeness and described as percentages and proportions.

**Analysis of Aim 1 Qualitative Data:** Qualitative data will be transcribed and analyzed in accordance with guidelines specified by NIH-Best Practices for Qualitative Research in the Health Sciences for applicability, preferences, clinical relevance, intervention length/timing, and challenges. Coding and categorizing the data will be followed by comparing and contrasting categories to identify overarching themes and similarities and dissimilarities among patients' experiences and perspectives. The evolving analysis will be tracked using memos and shared during regular study team meetings to enhance rigor and develop the findings and interpretations.

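### Does Primary Outcome 6 pool exercise-session ratings with the daily EMA prompts, and does the undefined base for Primary Outcomes 2 to 5 matter?

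*Combined protocol and SAP*

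**What the plan says.** Section 3.0, Primary Outcome 6, divides completed prompts "out of the total number of EMA survey prompts delivered to participants", from baseline to the 12-week assessment, and names no prompt type. Aim 1 in Section 1.0 lists a narrower indicator, "and daily EMA survey completion". The quantitative paragraph of Section 16.0 says that "daily ecological momentary assessment (EMA) completion will similarly be examined for completeness and described as percentages and proportions".

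Section 5.0 describes two streams from one app. The scheduled stream is a morning report and "2 additional prompts during the afternoon and evening". The second stream starts only when a participant signals the start of a session: "The RealLife mobile app will prompt participants to complete ratings of affective response to exercise at the start, during, and end of exercise". Section 12.0 prices the scheduled stream as "3 EMA prompts/day X 10 days X 4 data collection periods" and adds that "participants will not be paid for completing the during exercise EMAs reports".

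On people who leave, Section 13.0 has the team "continue attempts to contact participants for each session and study assessment unless and until they ask us" to stop. It does not say when app prompts end.

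Primary Outcomes 2 to 5 take participants with valid accelerometer data over those in the sample at each assessment, and the sample is not defined. The retention outcomes use those who enroll. Section 22.0 has two consents, and Section 11.0 counts its 30 participants at the second.

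**The concern.** Section 5.0 uses the verb prompt for the exercise ratings, and Section 12.0 calls them EMA reports. By that vocabulary the denominator of Outcome 6 takes them in. They are dense, unpaid and self-triggered, and their number rises with the behaviour that the intervention promotes. A pooled rate would mix willingness to answer surveys with exercise volume and give more weight to frequent loggers.

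Two further gaps seem to add to this. A denominator of delivered prompts might count a silent participant's unanswered prompts but drop those of someone who formally withdraws. For Outcomes 3 to 5, a base of people still present would show good wear compliance even if many had left. Since Aim 1 uses EMA completion and wear time as indicators of acceptability, an unclear denominator could change how the pilot is read.

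**Working it through.** **The plan's own count.** Section 12.0: 3 prompts x 10 days x 4 periods = 120 per participant. At $1 each this is $120, and with two surveys at $20 it gives the stated $160. For 30 participants with full delivery the denominator is 30 x 120 = 3,600. Exercise ratings play no part in this count.

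**What pooling would do.** A 30-minute session gives 6 alerts (every 5 minutes to 30) plus 1 afterwards, so 7, or 8 with a start rating. Assume 30-minute sessions, 90 minutes a week (the goal in Section 4.0), logging in the three follow-up bursts only, and an 80% daily rate (0.80 x 120 = 96 answered).

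- Sessions: 3 a week x 10/7 weeks x 3 bursts = 12.86.
- Exercise prompts E: 12.86 x 7 = 90.0, or 12.86 x 8 = 102.9.
- Share of all prompts, E/(120 + E): 90.0/210.0 = 43%, or 102.9/222.9 = 46%.
- Pooled rate, (96 + qE)/(120 + E), where q is the assumed response to exercise prompts:

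| q | E = 90.0 | E = 102.9 |
|---|---|---|
| 0.50 | 67.1% | 66.2% |
| 0.80 | 80.0% | 80.0% |
| 0.95 | 86.4% | 86.9% |

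At 30 minutes a week, E is 30.0 to 34.3, and the pooled rate is 73% to 74% (q = 0.50) or 83% (q = 0.95). The sign of the shift depends wholly on q, which the documents do not give.

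Logging across all 12 weeks would give larger shifts. However, the follow-up paragraph of Section 5.0 places EMA collection in 10-day periods at weeks 2, 6 and 12, so that scenario does not fit the plan.

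**Leavers, scheduled prompts only.** Take the plan's 30% attrition (9 of 30) and an assumed 80% response while active. If prompts stop on leaving, the rate is 80%. If they continue unanswered, it is 0.80 x (21 x 120 + 9k)/3,600, where k is the number of prompts received before leaving:

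- k = 90 (after week 6): 0.80 x 3,330/3,600 = 74%.
- k = 60 (after week 2): 0.80 x 3,060/3,600 = 68%.
- k = 30 (after baseline): 0.80 x 2,790/3,600 = 62%.

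The last figure needs all nine to leave straight after baseline and all to keep receiving prompts to week 12.

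**Wear base, Outcomes 3 to 5.** With 30% attrition, 21 of 30 remain. If 18 have valid data (assumed), the rate is 18/21 = 86% of those present or 18/30 = 60% of starters. Retention is 21/30 = 70%, and (18/21) x (21/30) = 18/30. The second rate follows from two that are already reported, provided that those present at a visit are those who complete it.

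**The case for a change.** The strongest case for a change is that the text of a primary outcome should stand by itself. Outcome 6 contains neither daily nor scheduled, Section 5.0 does use prompt for exercise ratings, and someone exporting all app records under Section 3.0 alone could pool the two streams. The remedy would be two words and no new data, and definitions are best fixed before the data are seen. The undefined sample and the two consent points leave the base for baseline wear and for retention open as well.

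The observation about wording stands. The inference that the analysis is likely to go wrong does not. Section 16.0 sets out the analysis and limits it to daily EMA. Section 12.0 uses the noun prompts for the scheduled set and calls the exercise ratings reports. No section points towards a pooled rate as the target.

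The point about leavers is weaker. Delivered is an operational base, so a prompt that is not sent is not counted. Section 13.0 concerns contact by staff, not app scheduling. Section 5.0 also has staff call anyone who answers nothing for 24 hours in a data collection period, so silence would be noticed early.

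For Outcomes 3 to 5 the natural reading is those still in the study, and the retention outcomes show the loss at the same visits. How many people sign only the first consent is not given, so the effect on baseline wear and retention cannot be sized. Reporting each rate with its numerator and denominator makes the choice visible. The absent rule for valid accelerometer data concerns the numerator and is a separate matter.

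**Conclusion.** No change follows. For Outcome 6 this is a loose phrase that Aim 1 and Sections 5.0, 12.0 and 16.0 resolve together: the denominator is the scheduled daily prompts, 120 per participant, and the rate then does not depend on exercise volume. The illustrated 66% to 87% around 80% is what pooling could do at 90 minutes a week. It rests on assumed session length, logging and response rates, has no fixed direction, and is zero if both prompt types are answered equally often.

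The treatment of leavers and the base for Outcomes 2 to 5 are reporting details that analysts can settle sensibly by stating n and N. In a descriptive single-arm pilot with no hypothesis test, acceptability threshold or progression rule on these rates, no formal decision depends on them. The conclusion assumes that the analysts follow Section 16.0 and report retention beside wear compliance, as the plan already provides. A tidier sentence in Outcome 6 would do no harm, but the planned analysis does not depend on it.

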## 5.0 Procedures Involved

**Study Design Overview:** Physically inactive breast cancer survivors be recruited to participate in a pilot study promoting adherence to recommended weekly physical activity guidelines for breast cancer survivors. All participants will receive a core exercise promotion intervention and their daily activity levels and feeling states (affect) will be measured using EMA and accelerometry over a 12-week period with measurement burst assessment at baseline and 2-, 6-, and 12-weeks follow-up.

**Study 1.**  $N = 30$  participants will receive the core exercise promotion intervention plus an affect-regulated exercise prescription (Affect-Rx) in this single-arm pilot. The ORBIT model recommends patient stakeholders be involved in the development of interventions intended to serve them as early as possible in the translational process, thus, this study will be used to modify and refine the intervention protocol and study assessment schedule to be acceptable to the target population of physically inactive, stage 0-III breast cancer survivors.

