## 11.0 Local Number of Subjects

Based on the PI's experience conducting exercise intervention studies, we conservatively estimate a 30% rate of attrition. Thus, in order to ensure we hit our target of  $N = 20$  intervention completers, recruitment will continue until  $N = 30$  participants provide informed consent to participate in the intervention portion of the study (see Consent Form Part 2).

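### Primary Outcome 6 pools EMA completion from baseline to week 12 into one rate, so it cannot show whether completion holds up across the four bursts

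*Combined protocol and SAP*

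**What the plan says.** Section 3.0, Primary Outcome 6, takes as its numerator the "survey prompts completed by participants during the study" and sets it "out of the total number of EMA survey prompts delivered to participants. Time Frame: Baseline through 12-weeks follow-up assessments". That is one rate for the whole study. The analysis plan (Section 16.0) adds only that EMA completion will be checked for completeness and summarised as percentages and proportions. It gives no breakdown by burst, no per-participant summary and no rule for people who withdraw.

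The neighbouring outcomes are built differently. Primary Outcomes 2 to 5 report valid accelerometer data separately at baseline and weeks 2, 6 and 12. Secondary Outcomes 3 to 5 report retention at weeks 2, 6 and 12 over those who enrolled.

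On purpose and schedule, Section 5.0 says that "this study will be used to modify and refine the intervention protocol and study assessment schedule to be acceptable" to the target population, and that "the RealLife app will deliver daily EMAs over 10-day periods during the baseline, 2-, 6-, and 12-week follow-up assessments". Section 12.0 gives the volume as "3 EMA prompts/day X 10 days X 4 data collection periods". On attrition, Section 11.0 says "we conservatively estimate a 30% rate of attrition", with recruitment running until 30 "participants provide informed consent to participate in the intervention portion of the study".

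**The concern.** EMA completion is one of the objective indicators that the plan will use to judge whether the schedule is acceptable. The useful question for refinement is whether people still answer at weeks 6 and 12 as they did at the start. A rate summed over all four bursts averages that question away. The accelerometer is worn over the same 10-day periods and is reported at each of them, and no reason is given for treating EMA otherwise.

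The denominator raises a second question. Delivered prompts equal scheduled prompts only if everyone keeps receiving them. Should delivery end when a person leaves, the unanswered later prompts never enter the rate, and those who stay carry up to four times the weight of someone who left after baseline (120 prompts against 30). The prespecified figure would then describe prompt-answering among those still present, not completion of the schedule by all who enrolled.

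**Working it through.** **Inputs from the documents**
- Scheduled daily prompts per person: 3 × 10 × 4 = 120, or 30 per burst (Section 12.0). At one dollar per prompt this reproduces the stated EMA payment of $120.
- 30 enrolled in the intervention portion, 20 completers wanted, 30% attrition (Section 11.0). Check: 20 / (1 − 0.30) = 28.6, rounded up to 29, which the plan's 30 covers. 30 × 0.70 = 21 remain and 9 leave.
- Total scheduled: 30 × 120 = 3,600.

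**Assumptions, not in the documents:** completion rates in each burst, and when the nine leave. Both are varied below.

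**Step 1. Masking of a decline, with no drop-out.** Each burst delivers 30 × 30 = 900 prompts, so the pooled rate is the plain average of the four burst rates.
- 90, 80, 70, 60%: 2,700 / 3,600 = 75.0%
- 95, 85, 70, 50%: 2,700 / 3,600 = 75.0%
- constant 75%: 2,700 / 3,600 = 75.0%

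Three different courses give the same reported value.

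**Step 2. Denominator, if delivery stops when a person leaves.** With n the number present and r the completion rate in each burst:
- rate as defined = Σ(n × 30 × r) / Σ(n × 30)
- rate over scheduled = Σ(n × 30 × r) / 3,600

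At a flat 80% among those present:

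| When the nine leave | Present at the four bursts | Delivered | Completed | As defined | Over scheduled | Gap (points) |
|---|---|---|---|---|---|---|
| all before week 2 | 30, 21, 21, 21 | 2,790 | 2,232 | 80.0% | 62.0% | 18.0 |
| gradually | 30, 27, 24, 21 | 3,060 | 2,448 | 80.0% | 68.0% | 12.0 |
| all before week 12 | 30, 30, 30, 21 | 3,330 | 2,664 | 80.0% | 74.0% | 6.0 |

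Between 270 and 810 of the 3,600 scheduled prompts (7.5% to 22.5%) are absent from the denominator.

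**Step 3. Denominator, if every leaver is still sent prompts.** Delivered is then 3,600, and the two rates coincide. In the gradual case both are 2,448 / 3,600 = 68.0%, and the gap is zero.

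**Step 4. Sensitivity to who leaves.** Suppose stayers complete 85% and leavers 60% until they go.
- All leave before week 2: completed 21 × 120 × 0.85 + 9 × 30 × 0.60 = 2,142 + 162 = 2,304. That is 2,304 / 2,790 = 82.6% as defined and 2,304 / 3,600 = 64.0% over scheduled, a gap of 18.6 points.
- All leave before week 12: 2,142 + 9 × 90 × 0.60 = 2,628. That is 2,628 / 3,330 = 78.9% against 2,628 / 3,600 = 73.0%, a gap of 5.9 points.

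**Step 5. What a by-burst report would show.** Take gradual loss, rates of 90, 80, 70, 60% among those present, and delivery stopping on leaving. The pooled rate as defined is 2,340 / 3,060 = 76.5%. By burst it is 90, 80, 70, 60% over delivered prompts and 90, 72, 56, 42% over scheduled prompts. The pair of series separates falling compliance from loss of participants.

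**The case against.** The strongest reply concerns the denominator. No section says that delivery stops. Section 5.0 has the app, once on the participant's own phone, delivering at all four bursts, and Section 13.0 keeps contact attempts going until the person asks to stop. Someone who goes silent may well still be sent prompts and count as a non-completer. This stands: the denominator effect is conditional and may be nil.

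Second, attrition is not hidden. Retention over those enrolled is a secondary outcome at weeks 2, 6 and 12, and accelerometer validity is reported at each time point. This also stands, but retention neither corrects the EMA rate nor shows falling completion among those who stay.

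Third, the consequence is limited. No EMA threshold exists. Refinement also draws on the acceptability questionnaire and on exit interviews coded for length, timing and challenges. EMA completeness is monitored during the study (Sections 5.0 and 17.0), and the analysis plan does not forbid a table by burst. All of this is fair. It still leaves the defined primary outcome as a figure that cannot show a decline.

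Fourth, scoring undelivered prompts as failures mixes retention with compliance, and would count a participant withdrawn for a medical event as not completing the schedule. This stands, and is why the scheduled-prompt rate should sit beside the delivered-prompt rate and not replace it.

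**Conclusion.** The point holds for the pooling. One rate from baseline to week 12 cannot distinguish a stable schedule from a failing one, and this needs no assumption about drop-out: very different courses all give 75.0%.

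The denominator effect is possible but not established. It runs from 0 to about 18 points at the plan's 30% attrition, or 18.6 if leavers also answer less than stayers. The upper end needs all nine to leave between consent to the intervention portion and the week 2 burst, with delivery stopping at once. The completion rates behind these figures are assumed, since the documents give none.

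Three stronger readings are tempting and not supported.
- A reader might infer that leavers do drop out of the denominator, so that acceptability is overstated. The documents are silent on delivery after leaving.
- A reader might infer that week-12 EMA data would be mostly missing. The plan's attrition alone does not give that: at 80% among those present, 21 × 0.80 / 30 = 56% of scheduled week-12 prompts are completed. The figure reaches 42% only if an assumed fall to 60% is added.
- A reader might infer that a burdensome schedule would be carried forward. With no threshold and several other sources of evidence, no decision is shown to change.

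**What to change.** In Primary Outcome 6, report completion of the daily prompts separately at baseline and weeks 2, 6 and 12, as is done for the accelerometer. For each burst give two figures side by side:
- prompts completed out of prompts delivered;
- prompts completed out of the 30 scheduled per enrolled participant.

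State how prompts after withdrawal, or after a participant goes silent, are counted in each. State also which of the two consent stages in Section 22.0 defines enrolled, because the baseline burst comes before the intervention starts. Limiting the outcome to the daily prompts also settles whether the during-exercise alerts described in Section 5.0 belong in the rate, which the present definition leaves open. Keep the pooled rate over delivered prompts as a supplementary figure.

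The cost is an edit to one outcome definition, a sentence in Section 16.0 and slightly more tabulation. No new data collection is needed, since each daily prompt already belongs to a known burst. The downside is that the reported figures may look less favourable than the single rate.
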